8.4.2 Behavioural data

When conducting t tests, degrees of freedom will be corrected where the assumption of equal variances between groups is violated (i.e. Levene's Test is significant). When conducting ANOVAs, the Greenhouse-Geisser procedure will be used to correct the degrees of freedom where assumptions of equality of variance are violated. The within-subjects factors for each task, and the contrasts tested in the ANOVA, are included in a table detailing the planned repeated measure ANOVA comparisons. Post hoc independent samples t tests will be performed to follow up any significant interactions found in ANOVAs.

If there is a significant group x condition interaction found, we will not use the Bonferroni correction for multiple comparisons.

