2. SYNOPSIS

Please state why this study is not considered a Clinical Trial of an Investigative Medicinal Product	This study is not a clinical trial as we are not investigating the efficacy of prucalopride, but rather using it as a probe to understand the role of 5-HT4 receptors in emotional processing. This study does not fit the MHRA definition of a clinical trial as one designed to: discover or verify/compare a drug's clinical effects; to discover or verify/compare its pharmacological effects (e.g. pharmacodynamics); to identify or verify/compare its adverse reactions; or to study its absorption, distribution, metabolism or excretion (https://www.gov.uk/government/uploads/system/uploads/attachment_data/file/31795 2/Algothrim.pdf)	
List all sites where study will be conducted	Department of Psychiatry, Warneford Hospital, University of Oxford Oxford Centre for Human Brain Activity (OHBA), Warneford Hospital, University of Oxford	
Age Range of Study Participants	18-40 years	
Planned Sample Size	50 healthy volunteers (25 per group)	
Planned Study Duration (n.b. A minimum approval period of 1 year and maximum of 5 years can be granted)	24 months	
Anticipated Start Date	1 st March 2018	
Anticipated End Date	1 st March 2020	
	Objectives	Outcome Measures
Primary	To investigate the effects of seven day prucalopride administration on 1. Recognition of positive and negative facial expressions 2. Performance on Auditory Verbal Learning Task	1. Accuracy (%) and reaction times on computer-based task of facial expression recognition (FERT), comparing those

	(AVLT)	2.	receiving drug and placebo. Number of words correctly recalled across blocks (and number of intrusions and repetitions)
Secondary	To investigate the effects of seven day prucalopride administration: 1. Amygdala response to emotional faces 2. Hippocampal response to novel versus repeated scenes 3. Reward sensitivity 4. Categorisation, recall and recognition of emotional words	1. 2.	in the amygdala during emotional faces task presentation BOLD fMRI signal in hippocampus to pictures of familiar versus novel scenes.
		4.	Number of positive and negative words correctly categorised, recalled, and recognised on emotional memory task

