The primary outcome measures are performance (accuracy and reaction time) in a computer-based task of facial expression recognition (FERT), and performance on the auditory verbal learning task AVLT, compared between drug and placebo groups. Secondary to this is the amygdala and hippocampal BOLD fMRI response to emotional faces and novel vs. repeated scenes respectively, reward sensitivity on the PILT, and number of positive and negative words correctly categorised, recalled, and recognised on emotional memory tasks. The tertiary outcome measures are reaction times to fearful vs. happy faces on the FDOT, BOLD fMRI response during resting state, performance (accuracy and reaction time) on the OMT task of visual short term memory, and relative/global cerebral blood flow using arterial spin labelling, all compared between those receiving drug and placebo.

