6.2 Objectives and Endpoints

These outcomes have been pre-registered on clinicaltrials.gov (NCT03572790). Primary outcomes are identified by bold typeface.

Objectives		Outcome measures / endpoints		
_	ate the effects of seven day e administration compared to			
Primary	Recognition of positive and negative facial expressions	Accuracy to recognise computer-based positive and negative facial expressions (anger, disgust, fear, happy, sad, surprise)		
		Misclassifications (number of responses to each facial expression category incorrectly classified as another facial expression category)		
		Reaction time to recognise facial expressions		
	Performance on Auditory Verbal Learning Task (AVLT)	Accuracy on AVLT (number of items correctly recalled across trials)		
		Number of intrusions (words incorrectly recalled) and number of repetitions (words repeated within the same trial)		
		Number of hits and false alarms in the delayed recognition test		
Secondary	Neural response to emotional faces	Blood Oxygen Level Dependent (BOLD) signal in areas including the amygdala, anterior cingulate cortex, and orbitofrontal cortex		
	Neural response to novel vs. repeated scenes	Blood Oxygen Level Dependent (BOLD) signal to scenes that have previously been seen compared to novel scenes in areas including the hippocampus and parahippocampal regions		
	Reward sensitivity as measured by the Probabilistic Instrumental Learning Task (PILT)	Amount won, amount lost, and total monetary amount earned Accuracy (correct or incorrect symbol choice) and proportion of group choosing correct symbol per trial		

Categorisation, recall, and recognition of emotional words on emotional memory	Emotional Categorisation Task (ECAT): accuracy and reaction time to classify positive and negative descriptor words
tasks	Emotional Recall Task (EREC): number of words correctly recalled (hits) and number of words incorrectly recalled (false alarms)
	Emotional Recognition Task (EMEM): accuracy and reaction time to correctly recognise positive and negative words (hits), and number of incorrectly recognised words (false alarms)
Vigilance to fearful and happy faces on the Facial Dot Probe Task (FDOT)	Vigilance scores derived from reaction time

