8.4.2.1 Primary outcomes

Facial Expression Recognition Task (FERT):

As in previous work (Harmer et al., 2004, Harmer et al., 2009), data will be analysed using repeated measures analyses of variance (ANOVAs). Group (prucalopride or placebo) will be the between-subject factor, and emotion (6 levels) will be the within-subject factor.

Auditory Verbal Learning Task (AVLT):

The number of correctly recalled words on the following trials will be calculated: List A immediate recall trials 1-5. A repeated measures ANOVA will be used to examine if there is an effect of prucalopride administration on word recall (between subject factor: group; within-subject factors: List A acquisition trial). Independent samples t-tests will be conducted to test if there is a group difference in the number of words accurately recalled after a short or long delay (List A short and long delay trials respectively, and the number of intrusions (incorrect words not present in list) and repetitions (correct words recalled more than once in the same acquisition trial) across List A acquisition trials. Independent samples t-tests will also be used to compare List B immediate recall and delayed recognition performance (number of hits and false alarms) between the groups.

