Task	Within Subject Factors	Number of Levels	Outcomes Used	Critical Contrasts Tested in the Analyses
FERT	Face Emotion	6 (Fear, anger, happy, surprise, disgust, sad)	% Accuracy Reaction time Misclassifications	Face emotion x treatment group
ECAT	Word Valence	2 (Positive, negative)	Accuracy Reaction time	Word Valence x treatment group
EREC	Word Valence Accuracy	2 (Positive, negative) 2 (Hits, false alarms)	Number of words recalled (correctly and incorrectly)	1. Word valence x treatment group 2. Word valence x accuracy x treatment group
EMEM	Word valence Accuracy	2 (Positive, negative) 2 (Hits, false alarms)	Number of words recognised (correctly and incorrectly) Reaction time	1. Word Valence x treatment group 2. Word valence x accuracy x treatment group
FDOT	Face Emotion Probe Duration	2 (Fearful, happy) 2 (Masked, unmasked)	Vigilance scores derived from reaction time	Face emotion x treatment group

				2. Face emotion x probe duration x treatment group
AVLT	/LT Trial 5 (List A acquisition tria 1-5)		Number of words recalled Number of intrusions Number of repetitions	Trial x treatment group
PILT	Trial type	2 (Win, loss)	1.Proportion of people choosing correct symbol	Trial type x treatment group
ОМТ	Trial 2 (1 probe, 3 probes)		 Proportion of correct probe selections Absolute error for probe location Reaction Time Proportion of misbinding errors 	1.Trial condition x treatment group

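### The SAP's table of tested contrasts omits the AVLT group main effect, which best matches that primary endpoint, and the stated power is for a direct fear test, not the planned gated procedure

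*SAP*

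**What the plan says.** **AVLT.** SAP 8.4.2 leaves the choice of contrasts to a table: "the contrasts tested in the ANOVA, are included in a table detailing the planned repeated measure ANOVA comparisons". The table stands at the end of SAP 8.4.2.2, with the column heading "Critical Contrasts Tested in the Analyses". Its AVLT row has one within-subject factor (List A acquisition trials 1-5), three outcomes (words recalled, intrusions, repetitions) and one contrast, "Trial x treatment group".

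Other places describe the analysis or endpoint as follows:

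- SAP 8.4.2.1: "A repeated measures ANOVA will be used to examine if there is an effect of prucalopride administration on word recall", with group as the between-subject factor.
- SAP 6.2: "Accuracy on AVLT (number of items correctly recalled across trials".
- Protocol section 2: "Number of words correctly recalled across blocks (and number of intrusions and repetitions".
- Protocol section 9: "performance on the auditory verbal learning task AVLT, compared between drug and placebo groups".

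For errors, SAP 8.4.2.1 assigns independent-samples t-tests to delayed recall "and the number of intrusions (incorrect words not present in list) and repetitions". The table puts intrusions and repetitions under the trial-by-group ANOVA.

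**FERT and power.** Protocol section 9 claims 0.9 power at 25 per group for fear accuracy (drug 10.64, SD 9.77; placebo 3.36, SD 5.96). SAP 4.5 cites the same study, says that 38 in total give 0.9 power at 0.05, and raises the number to 50. SAP 8.4.2 plans t-tests on single conditions as follow-up of a significant interaction.

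**Stratification.** SAP 4.3 stratifies randomisation by gender. No behavioural model includes it; SAP 8.4.3.3 only considers it as a confounder for the imaging analyses.

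**The concern.** The trial-by-group interaction and the group main effect answer different questions. The interaction asks whether the two groups' learning curves differ in shape; the main effect asks whether one group recalls more words over the five trials. A drug that raises recall equally on every trial leaves the interaction at its null value. A drug that does nothing on trial 1 and helps more with each repetition shows mainly in the interaction.

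For a primary outcome, the reader should know before unblinding which term bears on the endpoint. Here the table names one term, while the endpoint and text point more naturally to the other. The same data could then be reported as positive or negative depending on the term chosen. The differing methods for intrusions and repetitions leave a similar choice open.

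On FERT, the sample size is justified by a test of fear accuracy that the SAP plans only after a significant six-level interaction. The quoted power is therefore not the power of the planned procedure.

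**Working it through.** **1. The plan's own power figure.** Inputs are the means and SDs in protocol section 9.

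- Difference: 10.64 - 3.36 = 7.28.
- Pooled SD: sqrt((9.77² + 5.96²)/2) = 8.09.
- d = 7.28/8.09 = 0.90.
- Power at 25 per group, two-sided 0.05: 0.889 by normal approximation, 0.876 by noncentral t.

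The stated 0.9 is thus closely matched by a plain two-group test of fear accuracy with no gate.

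**2. The SAP's 38.** With the same d:

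- 19 per group: power 0.77 two-sided (0.86 one-sided).
- Needed for 0.9 by two-sided t-test: 27 per group, 54 in total (44 one-sided).
- 19 per group reaches 0.9 two-sided only if d is about 1.08.

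The SAP prints no effect size, so its inputs are unknown. The 38 does not follow from the protocol's figures.

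**3. AVLT, List A trials 1-5.** The documents give no AVLT effect size or trial correlation, so these are assumptions: unit SD on each trial, equal correlation ρ between trials (0.4, 0.6, 0.8), n = 25 per group, two-sided 0.05.

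- Main effect: two-sample t-test on the five-trial mean, standardised effect = mean d / sqrt((1 + 4ρ)/5). The divisor is 0.721, 0.825, 0.917.
- Interaction: F on 4 and 192 df, noncentrality λ = (25/2) × Σ(d_j - mean d)² / (1 - ρ).

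For a uniform gain every d_j equals the mean, so λ = 0 and the rejection rate is 0.05. For a gain rising linearly from 0 to 0.8, Σ(d_j - mean d)² = 0.16 + 0.04 + 0 + 0.04 + 0.16 = 0.40, so λ = 5/(1 - ρ) = 8.33, 12.5, 25.

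| Assumed gain | Trial × group (ρ 0.4 / 0.6 / 0.8) | Group main effect (ρ 0.4 / 0.6 / 0.8) |
|---|---|---|
| Uniform d 0.5 | 0.05 / 0.05 / 0.05 | 0.671 / 0.556 / 0.472 |
| Uniform d 0.8 | 0.05 / 0.05 / 0.05 | 0.970 / 0.919 / 0.856 |
| 0.4 rising to 0.8 | 0.174 / 0.248 / 0.477 | 0.822 / 0.713 / 0.621 |
| 0.2 rising to 1.0 | 0.613 / 0.810 / 0.988 | 0.822 / 0.713 / 0.621 |
| 0 rising to 0.8 | 0.613 / 0.810 / 0.988 | 0.485 / 0.390 / 0.327 |

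Neither term is better throughout. A simulation with Greenhouse-Geisser correction agrees: for a uniform gain of d 0.5 and ρ 0.3, 0.5, 0.7, the interaction rejects in about 5% and the main effect in 74%, 60% and 50%.

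**4. The gate on fear.** Simulated power to reach significance on both the interaction and the fear t-test, with d = 0.90 on fear and correlation between emotions from 0 to 0.7 (both patterns and correlations assumed):

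| Pattern in the other five emotions | Gated power |
|---|---|
| Other negatives move half as much, happy and surprise half as much the opposite way | 0.84-0.88 |
| No movement | 0.56-0.88 |
| All move half as much in the same direction | 0.16-0.46 |

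The direct test has 0.876 in every case, so the cost of the gate runs from negligible to large.

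**The case against.** **The endpoint wording is not decisive.** Neither SAP 6.2 nor the protocol synopsis says total or sum, and making trial a within-subject factor also fits an interest in the learning curve. That stands: the main effect is the more natural reading, not the only one.

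**A reader might infer that the main effect has been dropped.** The documents do not support this. Group is in the ANOVA, so its main effect will appear in the output, and the table's heading speaks of critical contrasts without saying that no others are tested. Delayed recall, List B recall and recognition have direct t-tests and are unaffected.

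**A reader might infer from the earlier single-dose study that a uniform gain on immediate recall is expected.** Protocol section 4 reports more words remembered but does not say on which AVLT measure, so it cannot settle the pattern.

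**A reader might infer that FERT is underpowered.** This does not follow. The gated ranges rest on the protocol's effect size. If the SAP's 38 is taken at face value (d about 1.08), the direct test at 25 per group has power 0.96, and the gated fear-only range becomes 0.76-0.96. The SAP also raised its number deliberately, from 38 to 50.

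**A reader might treat the lack of a joint rule for FERT and AVLT as an error.** One independent 0.05 test per task gives 1 - 0.95² = 9.75%. But these are separate objectives in a study stated not to test efficacy, and Holm or separate testing is a matter of judgement. The SAP marks primary outcomes in bold, which the available text does not show, so the ranking of measures within each task cannot be judged either.

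**Conclusion.** The point holds as a conflict between table, text and endpoint. For List A immediate recall, the table to which SAP 8.4.2 refers omits the contrast that best matches the primary endpoint. Under the assumed correlations and 25 per group, the interaction has no power beyond its 5% error rate for a uniform gain, while the main effect has 0.472-0.970 for d 0.5-0.8. The advantage reverses if the gain starts near zero and grows. The conflict over intrusions and repetitions rests on the text alone and needs no assumption.

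The stated 0.9 describes a direct fear comparison (0.876 by t-test) and not the gated procedure. How much power the gate costs cannot be fixed from the documents. The SAP's 38 and the protocol's means and SDs do not agree under a two-sided test, nor under a one-sided one. Leaving gender out of the behavioural models is a minor omission. This should be fixed, but it does not show that the trial is unsound.

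**What to change.** 1. **AVLT row of the table.** Add the group main effect on List A trials 1-5 as the contrast matching the endpoint, and keep trial by group as the learning-rate contrast. Use the direct two-group comparisons of SAP 8.4.2.1 for intrusions and repetitions in both places. Cost: if the conclusion rests on the main effect, power is lower when the gain starts near zero and grows (0.327-0.485 against 0.613-0.988 for d 0 to 0.8).
2. **Gender.** Include it in the behavioural models, as randomisation is stratified by it. Where a t-test is planned, the equivalent linear model with group and gender serves. Cost: one degree of freedom per model.
3. **Power statement.** Say in SAP 4.5 that the power refers to a direct two-group test of fear accuracy and not to the interaction-gated procedure. Report the fear comparison with its 95% confidence interval whatever the interaction shows. Give the effect size behind the 38 and reconcile it with the protocol's figures. Label any gated power as dependent on assumed effect patterns and correlations.
4. **Timing.** Date the change and state the blinding status. SAP 5.2 shows that work on the imaging faces data had begun before the December 2020 amendment and records a further amendment in October 2022. If the change comes after unblinding, report the changed analyses as sensitivity analyses beside the plan as it stands.

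No new data are needed. The cost is a dated SAP amendment, with the registry and ethics steps that SAP 5.2 describes for the change in outcome hierarchy.

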8.4.2.1 Primary outcomes

Facial Expression Recognition Task (FERT):

As in previous work (Harmer et al., 2004, Harmer et al., 2009), data will be analysed using repeated measures analyses of variance (ANOVAs). Group (prucalopride or placebo) will be the between-subject factor, and emotion (6 levels) will be the within-subject factor.

Auditory Verbal Learning Task (AVLT):

The number of correctly recalled words on the following trials will be calculated: List A immediate recall trials 1-5. A repeated measures ANOVA will be used to examine if there is an effect of prucalopride administration on word recall (between subject factor: group; within-subject factors: List A acquisition trial). Independent samples t-tests will be conducted to test if there is a group difference in the number of words accurately recalled after a short or long delay (List A short and long delay trials respectively, and the number of intrusions (incorrect words not present in list) and repetitions (correct words recalled more than once in the same acquisition trial) across List A acquisition trials. Independent samples t-tests will also be used to compare List B immediate recall and delayed recognition performance (number of hits and false alarms) between the groups.

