9. STATISTICS AND ANALYSIS

Do you have a statistical plan?	Yes X	No 🗌
If no, please justify.		
The IBM SPSS statistical software will be use to analyse all behavioural data.		
Demographic and baseline measures will be analysed using independent t-tests.		
Mood, anxiety, and side effect measures will be analysed using repeated measures analysis of variance (ANOVA).		
Behavioural task results will be analysed using between-groups analysis of variance (ANOVA).		
Any significant interactions will be followed up using simple main effect analyses. When assumptions of equality of variances are not fulfilled, the Greenhouse-Geisser procedure will be used to correct the degrees o freedom.		
Analysis of fMRI endpoints will be completed using the FSL software package.		
Number of Participants		
50 healthy volunteers (25 per group)		

Have you done a sample size calculation?	Yes 🖂	No 🗌
If yes, please give details below		
If no, please give details to indicate you have considered the implications the selected		
sample size will have on the study outcome		
We will be using the Emotion Test Battery, which is a well validated set of emotional proces sensitive to antidepressant effects. On the facial expression recognition task, one of the magnitudes is accuracy at recognising fearful facial expressions and a sample size of 25/group power to detect changes of the magnitude of those we have seen in a previous antidepres volunteer study [drug mean 10.64 (SD 9.77) vs. placebo mean 3.36 (SD 5.96) from Harmer Psych; ref 6].	nain outcom would give sant healthy	e e 0.9 y
Analysis of Outcome Measures		
Data analysis will take place at the University of Oxford, Department of Psychiatry and will be undertaken by the research team under the supervision of the Principal Investigator. All data will be analysed using a between-groups analysis of variance (ANOVA). Analysis of fMRI endpoints will be completed using the FSL software package.		·

Withdrawn participants' data will not be included in the analysis.

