4.5 Determination of Sample Size

We will be using the Emotional Test Battery, which is a well validated set of emotional processing tasks that are sensitive to antidepressant effects. On the facial expression recognition task (FERT), one of the main outcome variables is accuracy at recognising fearful facial expressions and this is the variable used for power calculations. Based on data acquired in (Harmer et al., 2004) comparing citalopram to placebo, if we aim for 0.9 power and a 0.05 false positive rate, a suggested total sample size is 38 (G*power) to ensure determination of group level differences at this variable if they exist. As 5HT₄ agonism is less well studied and the dose required of prucalopride for optimal agonism at the receptor is uncertain, we will aim for 25 individuals per group (total sample size of 50).

5. Changes in the Conduct of the Study or Planned Analyses

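### SAP 8.4.2.1 lists eight AVLT group comparisons as primary with no correction, order or success rule; if any one at 0.05 could carry the claim, the false-positive chance is about 12–34%

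*SAP*

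**What the plan says.** The AVLT is one of two primary domains. Its measures are described in several places.

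- **Protocol synopsis:** "Number of words correctly recalled across blocks (and number of intrusions and repetitions", with the last two in brackets. Protocol section 9 names only performance on the task.
- **SAP 6.2, Primary rows:** first "Accuracy on AVLT (number of items correctly recalled across trials", then intrusions and repetitions, then hits and false alarms in delayed recognition. That makes five measures. Delayed recall and List B have no separate entry. The section says primary outcomes are in bold.
- **SAP 8.4.2.1, headed Primary outcomes:** "A repeated measures ANOVA will be used to examine if there is an effect of prucalopride administration on word recall", using List A trials 1–5. Separate t-tests follow for a "group difference in the number of words accurately recalled after a short or long delay", for intrusions and for repetitions. Finally, "t-tests will also be used to compare List B immediate recall and delayed recognition performance (number of hits and false alarms) between the groups".
- **SAP table of planned repeated measures comparisons:** the AVLT row gives trial by treatment group as the critical contrast, for words recalled, intrusions and repetitions.

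On multiplicity, SAP 8.4.2 says only that Bonferroni will not be used once a group by condition interaction is significant. SAP 8.4.3.4 deals with image data. A 0.05 level appears for behavioural tests only in the sample-size section, SAP 4.5: "if we aim for 0.9 power and a 0.05 false positive rate, a suggested total sample size is 38 (G*power".

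**The concern.** The seven t-tests in 8.4.2.1 are planned outright. They do not depend on a significant interaction, so the Bonferroni sentence in 8.4.2 does not deal with them. Nothing in the section says which result decides whether prucalopride affected verbal memory. An isolated difference in repetitions or List B recall could therefore be reported as a primary finding on the same footing as a difference in List A learning.

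Two features make this more than a formality. The group's single-dose study reported more words remembered on prucalopride, so a memory result is a likely headline. And the sample size rests on recognition of fearful faces, so no AVLT measure was singled out by a power calculation.

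**Working it through.** **1. The plan's own figure.** The documents give no error rate for the AVLT. The only figure to reproduce is the power for fearful-face accuracy in Protocol section 9, from "drug mean 10.64 (SD 9.77) vs. placebo mean 3.36 (SD 5.96".
- Difference: 10.64 − 3.36 = 7.28.
- Pooled SD: √[(9.77² + 5.96²)/2] = 8.09, so d = 0.90.
- With 25 per group: 7.28 / (8.09 × √(2/25)) = 3.18, and power = Φ(3.18 − 1.96) = 0.889. The noncentral t gives 0.876.

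This agrees with the stated 0.9 to within about two points at two-sided 0.05. It supports reading 0.05 as two-sided, but it says nothing about the AVLT.

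**2. Count of AVLT comparisons in 8.4.2.1.** (1) List A trials 1–5; (2) short-delay recall; (3) long-delay recall; (4) intrusions; (5) repetitions; (6) List B recall; (7) recognition hits; (8) recognition false alarms. The List A ANOVA is counted once. Counting its group effect and its trial by group interaction separately makes nine.

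**3. Chance of at least one false positive, independent tests.** With k tests at 0.05 and no drug effect, this is 1 − 0.95^k.
- k = 5 (measures in SAP 6.2): 1 − 0.774 = 22.6%
- k = 8: 1 − 0.663 = 33.7%
- k = 9: 1 − 0.630 = 37.0%

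**4. Correlated tests.** The measures come from one task, so independence is an upper case. The documents give no correlations, so a common correlation r is assumed and varied. With c = 1.96 and X standard normal, the chance is 1 − E{[Φ((c − √r·X)/√(1−r)) − Φ((−c − √r·X)/√(1−r))]^k}, by numerical integration.

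| Assumed r | k = 5 | k = 8 | k = 9 |
|---|---|---|---|
| 0 | 23% | 34% | 37% |
| 0.3 | 21% | 30% | 33% |
| 0.5 | 18% | 25% | 27% |
| 0.7 | 15% | 19% | 20% |
| 0.9 | 10% | 12% | 12% |

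**5. Checks.** Simulated t-tests on eight normal measures, 25 per group ("we will aim for 25 individuals per group (total sample size of 50"), gave 33.7%, 29.9% and 25.2% at r = 0, 0.3 and 0.5. A less uniform pattern, with recall measures and hits correlated 0.5–0.8 and the error counts only weakly correlated, gave about 25–30%. Error counts are unlikely to be normal, so these are approximations.

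**6. Consistency between sections.** SAP 6.2 lists five AVLT measures and 8.4.2.1 tests eight. The ANOVA table places intrusions and repetitions under a trial by group contrast, while 8.4.2.1 gives each a t-test. Neither difference depends on what is in bold.

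**The case against.** The strongest reply is that section 6 defines the endpoints and section 8 only describes analyses task by task; SAP 8.4 itself refers back to section 6 for endpoint details. If the bold type in 6.2 marks accuracy alone, a deciding measure already exists. This cannot be excluded, because type weight is lost in the extracted text. A reader might infer from the 8.4.2.1 heading that all eight are primary whatever the bold shows, but no passage says the heading prevails. What remains is that 8.4.2.1 calls delayed recall and List B primary while 6.2 does not list them separately.

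The table's critical contrast is also a stated priority. It covers three outcomes, however, so it does not pick one.

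A reader might further infer that the SAP sets every AVLT test at an uncorrected 0.05. It does not say so. Waiving Bonferroni after a significant interaction may even imply its use otherwise. The text is ambiguous, and the calculation above is conditional on that reading. Likewise, no passage says that any one of the eight is enough; the documents are silent on the rule.

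The longer list in the SAP might be taken as an undisclosed widening of the primary outcome. That is not supported: Protocol section 9 is broad enough to include delayed recall, List B and recognition, and SAP 5.2 discloses a revised outcome hierarchy, a registry update and resubmission to the ethics committee.

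Finally, the study is presented as a mechanistic probe and not an efficacy trial. That lowers the stakes, but a result labelled primary still needs a known error rate.

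**Conclusion.** The point holds in conditional form. SAP 8.4.2.1 places eight AVLT comparisons under a primary heading and states no correction, order or success rule. If each is tested at two-sided 0.05 and any one can support a primary AVLT claim, the chance of a false claim is about 12–34%, or 2.4 to 6.7 times 0.05. Restricting the set to the five measures in 6.2 still gives about 10–23%.

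A single headline of 25% is tempting but would overstate what is known: it needs a common correlation of about 0.5, which is an assumption. That no AVLT measure is named as deciding also cannot be confirmed until the bold type in 6.2 is checked. Whatever that shows, 6.2, 8.4.2.1 and the ANOVA table must be reconciled. This should be corrected, and the correction is cheap.

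**What to change.** In SAP 6.2, 8.4.2.1 and the ANOVA table:

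1. Make words recalled over List A trials 1–5 the single deciding AVLT primary measure. It comes first in the synopsis, 6.2, 8.4.2.1 and the table, so the choice follows the documents' own order.
2. Name one deciding contrast, the group main effect, with trial by group supportive. This matches the question put in 8.4.2.1; a benefit of equal size on every trial would appear in the main effect and not in the interaction. If both contrasts count, that ANOVA alone carries 1 − 0.95² = 9.75% when they are independent.
3. Label the other seven measures supportive, report Holm-adjusted p-values (smallest p against 0.05/7 = 0.0071), and let none of them alone support a primary AVLT claim.
4. State one analysis for intrusions and repetitions, for example the 8.4.2.1 t-tests, and remove them from the ANOVA row.
5. Date the change and state whether AVLT data had been unblinded. SAP 5.2 records amendments in December 2020 and October 2022 but gives no unblinding date. If the data had been unblinded, do not select one measure; apply Holm across all eight in reporting (smallest p against 0.05/8 = 0.00625).

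The cost is SAP wording, and no analysis is dropped. The downside is that an isolated effect on delayed recall, recognition, List B or error counts could no longer be called a primary finding.
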